CTT  
CTT1403 Phase 1

Name of Sponsor Cancer Targeted Technologies, Inc.
Name of Investigational Products CTT1403 –  Lu-PSMA targeting therapeutic agent CTT1057 –  F-PSMA targeting diagnostic agent, or  Ga-PSMA-11
Title of Study Phase 1 Dose Escalation/Expansion Study of CTT1403 in Patients with Metastatic Castration-Resistant Prostate Cancer (mCRPC).
Study Phase Phase 1
ClinicalTrials.gov Identifier NCT03822871
Study Center(s): University of California San Francisco
Principal Investigator Confidential
Date March 2, 2021
Study Objectives Primary Objectives Dose-Escalation Period 

• Determine the safety and tolerability of CTT1403.

• Determine the dose-limiting toxicity (DLT) and maximum tolerated dose (MTD) following a single dose

 Dose-Expansion Period 

• Determine the preliminary antitumor activity of CTT1403 in patients with mCRPC as measured by objective tumor response by Response Evaluation Criteria in Solid Tumors (RECIST) 1.1 in accordance with Prostate Cancer Working Group 3 (PCWG3) criteria.

 Secondary Objectives 

• Characterize the organ dosimetry and pharmacokinetics of CTT1403

• Determine the change from baseline in patient reported pain as assessed by Brief Pain Inventory (BPI)

Study Endpoints Primary Endpoints Dose-Escalation Period 

• Frequency of DLTs at escalating dose levels of CTT1403 during Cycle 1 (6-week period)

 Dose-Expansion Period 

• Objective response rate by RECIST 1.1

• Adverse event profile by CTCAE v5 criteria

 Secondary Endpoints 

• Assessment of PK (distribution and elimination t1/2)

• Assessment of organ dosimetry of CTT1403 by SPECT/CT imaging at various timepoints

• Change from baseline in patient reported pain as measured by Brief Pain Inventory (BPI)

During treatment, patients in both stages of the study will attend study center visits and have study evaluations performed as detailed in the schedule of events. All study visits will be conducted on an outpatient basis with monitoring as indicated above.

Patients may continue to receive study drug until any of the following events: the development of radiographic or clinical disease progression, unacceptable toxicity, another discontinuation criterion is met, withdrawal of consent, closure of the study by the Sponsor, or receipt of two doses of CTT1403. Patients with prostate-specific antigen (PSA)-only progression in the absence of radiographic or clinical progression should continue to receive protocol therapy per PCWG3 guidelines.

CTT  
CTT1403 Phase 1

After discontinuation of CTT1403 treatment, patients will complete an EOT visit within 42 days after their last dose of study drug. The EOT visit will include a safety assessment; additional follow-up may be required if study drug-related AEs have not resolved at that time. Patients who discontinue study drug for reasons other than for PD will also be assessed for clinical evidence of disease progression. Patients without evidence of PD at the EOT visit and who do not start another therapy will be followed every 4 weeks up to 12 weeks, and again 6 months after final dose.

During the dose-escalation and expansion period, biopsy of tumor metastasis is optional at screening and disease progression.

Serial blood samples for PK will be collected from all patients in the dose-escalation period during Cycle 1 and on Day 1 of Cycle 2.

Organ dosimetry will be assessed by SPECT/CT imaging at the specified timepoints in the Study Calendar.

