#### **Duration of Treatment and Study Participation**

Patients will be administered CTT1403 once every 6 weeks for up to two doses in the absence of disease progression by PWCG3 criteria, unacceptable toxicity, another discontinuation criterion is met, withdrawal of consent, or closure of the study by the Sponsor.

Following completion of treatment, patients will undergo EOT assessments 30 (+ 7) days after their last dose of study drug, and will continue to be followed via telephone for survival status and clinical evidence of disease progression.

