**Duration of Treatment and Study Participation**

In the absence of treatment delays due to AEs, treatment be administered every 6 weeks, for up to 2 doses or until one of the following occurs:

1. Disease progression
2. Inter-current illness that prevents further administration of treatment
3. Unacceptable AE(s)
4. Patients decides to withdraw from the study
5. Significant patient non-compliance with protocol
6. General or specific changes in the patients' condition render the patient unacceptable for further treatment in the judgment of the investigator.
7. The patient has received 2 doses of CTT1403
8. A second dose of CTT1403 will not be given if the estimated cumulative kidney exposure exceeds 23Gy as determined by SPECT dosimetry following the first dose of CTT1403.

Following completion of treatment, patients will undergo EOT assessments 42 (+ 7) days after their last dose of study drug and will continue to be followed every 4 weeks up to 12 weeks and at 6 months post-treatment. Patients not exhibiting PD at the EOT assessment will be contacted every 90 days following final CTT1403 administration to report on disease progression for up to 6 months after last dose of study drug. Patients will undergo physical examination and lab donation of blood for assessment of CBC and creatinine every 4 weeks thereafter for 12 weeks after the last dose, until patient withdrawal from study, or death, whichever occurs first. Upon observation of delayed CBC recovery or other demonstration of drug related toxicity, the long-term observation period will be extended until recovery is observed and/or toxicities are resolved. Patients removed from study for unacceptable treatment related AEs will be followed until resolution or stabilization of all treatment related AEs Grade 2 or above.

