#### Prohibited Medications/Therapies

Enrolled patients may not receive investigational or approved anticancer agents including cytotoxic chemotherapy agents, anticancer tyrosine kinase inhibitors, or therapeutic monoclonal antibodies not included as a study drug on this protocol for the duration of participation. Palliative radiation is not permitted during study enrollment.

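### The TEAE table stops 30 days after the last dose although AEs are collected for 3 months, and the EOT day and follow-up population differ between sections

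*Combined protocol and SAP*

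**What the plan says.** Two sections carry the heading Duration of Treatment and Study Participation. Below, the first is the one just before Number of Patients, and the second is the one just after Investigational Product, Dosage, and Mode of Administration.

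**AE collection and summary.** Safety Assessments runs AE reporting from the start of study drug to 3 months after the last dose. The Safety part of Statistical Methods tabulates TEAEs by system organ class and preferred term, but only to 30 days after the last dose. The summaries by grade and causality, of DLTs, of Grade 3 and 4 AEs, of SAEs and of laboratory abnormalities carry no stated time limit. Study Endpoints lists AE profile as a primary endpoint of the expansion period.

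**EOT visit.**
- Study Design: "patients will complete an EOT visit within 42 days after their last dose of study drug".
- First Duration section: "EOT assessments 30 (+ 7) days after their last dose of study drug".
- Second Duration section: "EOT assessments 42 (+ 7) days after their last dose of study drug".

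**Follow-up after EOT.**
- Study Design: "Patients without evidence of PD at the EOT visit and who do not start another therapy will be followed every 4 weeks". This runs to week 12, with a further follow-up at 6 months, and no test is named.
- First Duration section: patients "will continue to be followed via telephone for survival status and clinical evidence of disease progression".
- Second Duration section: "Patients will undergo physical examination and lab donation of blood for assessment of CBC and creatinine every 4 weeks thereafter". The stated span is 12 weeks from the final dose, and the only reasons listed for stopping are given in these words: "until patient withdrawal from study, or death, whichever occurs first". Here freedom from progression is a condition only for the 90-day contact about progression.

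**The concern.** CTT1403 is a first-in-human lutetium-177 agent. The protocol itself expects late effects to matter: it plans blood counts and creatinine to 12 weeks, extends observation if counts recover slowly, and withholds the second dose on estimated kidney exposure. A TEAE table that closes at day 30 omits AEs that the sites will already have reported, in the main tabulation of a primary expansion endpoint. It also closes before the 6-week cycle opened by the last dose has ended.

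The visit rules are a separate matter. A site that follows one Duration section on the EOT day departs from the other. A patient who has progressed, or who has started new therapy, is outside the 4-weekly follow-up in Study Design but inside it in the second Duration section. Blood counts and creatinine after EOT could then depend on which section a site reads.

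**Working it through.** All days are counted from the last dose. The plan gives no figure of its own to reproduce.

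**Inputs.** AE reporting ends at 3 months (Safety Assessments); I take this as 91 days, with a range of 90 to 92. The TEAE summary ends at day 30 (Statistical Methods). A cycle, and the DLT window, is 6 weeks = 42 days (Study Design; Definition of Dose-Limiting Toxicity). At most two doses are given, 6 weeks apart.

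**Days outside the TEAE table.**
- After the last dose: 91 − 30 = 61 days; 61/91 = 67%. Range: 60/90 = 66.7% to 62/92 = 67.4%.
- Whole reporting period, two doses on schedule: 42 + 91 = 133 days; 61/133 = 46%.
- Whole reporting period, one dose: 91 days, so the share is 67%.
- Cycle opened by the last dose: 42 − 30 = 12 days outside, 12/42 = 29%. For a one-dose patient these are days 31 to 42 of the DLT window itself.

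**EOT windows.**

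| Section | EOT days | EOT days later than day 30 |
|---|---|---|
| Study Design | 0 to 42 | 12 of 43 |
| First Duration section | 30 to 37 | 7 of 8 |
| Second Duration section | 42 to 49 | 8 of 8 |

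- Study Design and first Duration section: days 30 to 37 are common, so these two agree.
- Study Design and second Duration section: day 42 only.
- First and second Duration sections: no common day.
- All three: no common day.

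Under the second Duration section, the EOT visit comes 42 − 30 = 12 to 49 − 30 = 19 days after the TEAE table has closed.

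**Laboratory visits after EOT (second Duration section, to day 84).** Counted 4-weekly from EOT, there is one visit, between 42 + 28 = day 70 and 49 + 28 = day 77. Counted 4-weekly from the last dose, there are two, on days 56 and 84. On either count, every one falls after day 30.

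**Follow-up population.** Study Design and the second Duration section share the same schedule: 4-weekly to 12 weeks, then 6 months. They differ on who is in it. Study Design requires no progression at EOT and no new therapy. The second Duration section sets neither condition for the examination and blood tests.

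**The case against.** A 30-day TEAE table beside longer AE collection can be a deliberate choice. AEs after day 30 are still reported, and the other AE and laboratory summaries have no stated limit, so late cytopenias and creatinine rises have a place elsewhere. This stands. It means that the table needs a companion, not that data are lost. It does not explain why the only summary with a stated window closes inside the treatment cycle.

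A reader might infer that the three sections are incompatible throughout, on EOT day, population and tests. The text does not support that. Study Design and the first Duration section agree on the EOT day. Study Design names no tests, so it cannot conflict over them. Telephone contact for survival and progression does not exclude clinic visits. The sections can be read cumulatively, although nothing says they should be.

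A reader might also infer that some or all patients go without safety visits from EOT until AE reporting ends: at least 91 − 42 = 49 days under Study Design, or 54 to 61 days under the first Duration section. Those gaps arise only if the second Duration section is disregarded, and nothing gives the other sections precedence over it. Other safeguards also remain: a safety assessment at EOT, possible further follow-up of unresolved drug-related AEs, and follow-up to resolution or stabilisation for patients removed because of unacceptable related AEs.

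Finally, Study Assessments defers to a schedule of events that is not in the text available here. It may settle visits and tests, and then only the wording needs aligning. Nothing suggests that it would alter the 30-day window set in Statistical Methods.

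**Conclusion.** The point holds in three limited parts.

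1. The TEAE table omits about 61 of 91 days after the last dose (67%), or 46% of the full reporting period for an on-schedule two-dose patient. This follows whichever EOT rule governs and rests only on taking 3 months as about 91 days. The EOT visit is certain to fall outside the table only under the second Duration section; an EOT visit by day 30, which the other two rules allow, falls inside it.
2. The EOT windows of the two Duration sections cannot both be met.
3. Study Design limits 4-weekly follow-up by progression and new therapy; the second Duration section does not.

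It would be too strong to say that safety is understated by a known amount. The documents give no late-toxicity rate and no fraction of patients progressing by EOT, so the number of AEs affected cannot be computed. DLT counts and the escalation rule are unaffected. The change is worth making because it concerns a primary expansion endpoint and costs little; the TEAE window is the more important part, and the visit rules are mainly a matter of alignment.

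**What to change.** 1. In Statistical Methods, add an AE summary through the 3-month reporting period beside the 30-day TEAE table, and show the start date of any new anticancer therapy. The days left out then fall from about 61 to 0, and EOT at days 42 to 49 and the later laboratory visits are covered.
2. Use one EOT window, 42 (+7) days, in Study Design and both Duration sections.
3. State that the physical examination, CBC and creatinine to 12 weeks after the last dose apply to all treated patients regardless of progression. Limit the condition in Study Design, and the telephone contact in the first Duration section, to progression and survival follow-up.

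The cost is about a sentence in each affected section and one extra table from data already collected. The blood draws, one or two per patient after EOT, are those the second Duration section already calls for. The real downside is that AEs arising after new therapy starts are harder to attribute to CTT1403, which is why the 30-day table should stay and the new-therapy dates should be shown.

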**Dose-Escalation Period**

It is estimated that up to 10 dose levels will be evaluated during the dose-escalation period of the study using an accelerated scheme for the first 3 doses (n=1/dose level), followed by a 3+3 dose escalation scheme for the final 7 doses. One patient will be enrolled at each of the first 3 dose levels. If a Grade  $\geq 2$  treatment-related AE is experienced during the DLT window of 6 weeks, then dose escalation schema will convert to a 3+3 design. Starting with enrollment of dose level 4, the study will convert to a 3+3 dose design, if not initiated sooner. All safety data from all patients enrolled in each cohort will be reviewed by the Data Safety Monitoring Committee (DSMB), with members minimally including the Principal Investigator and Sponsor, and sponsor Medical Monitor, to confirm any DLTs that were experienced, and to make a determination regarding enrollment in the next cohort. Based on the evaluation of the data, it may be decided that enrollment at an intermediate dose level or alternative dosing schedule not specified in the protocol will take place. If < 33% of patients (i.e., 0 of 1 (dose level 1-3) or 0 of 3 (dose level 4-10), 1 of 6 patients (all dose levels requiring additional enrollment) within a cohort have a DLT within the DLT window, then enrollment of the next cohort may commence with approval from the Medical Monitor. If  $\geq 33\%$  of the patients ( $\geq 2$  of up to 6 patients) within a cohort experience a DLT in the DLT window, then the MTD will have been exceeded and the previous dose level will be considered the MTD.

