***Definition of Dose-Limiting Toxicity***

A DLT is defined as any of the following AEs occurring during Cycle 1 (6-week length), regardless of Investigator attribution to CTT1403, unless the AE can be clearly attributed to an extraneous cause (e.g., disease progression):

- Grade 4 neutropenia lasting  $> 5$  consecutive days.
- Grade 3 or 4 febrile neutropenia.
- Grade 4 thrombocytopenia lasting  $\geq 7$  days, or Grade 3 or 4 thrombocytopenia with clinically significant bleeding or requirement for platelet transfusion.
- Any nonhematologic AE  $\geq$  Grade 3, with the exceptions of Grade 3 nausea, vomiting, diarrhea, electrolyte abnormality, constipation, fever, fatigue, or skin rash that resolves to Grade  $\leq 2$  within 72 hours with optimal medical management.
- Any other treatment-related toxicity that results in delay of Cycle 2 administration of CTT1403 by  $> 21$  days and/or toxicity considered by the Investigator and Sponsor's medical representatives to be dose-limiting.

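### The stopping rule's percentage and count disagree at 1 DLT in 3 and 1 in 1, and the Cycle 2 delay DLT, unless declared earlier, is established about three weeks after the next cohort may open

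*Combined protocol and SAP*

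**What the plan says.** Dose-Escalation Period gives two lists. The next cohort may open when fewer than 33% of patients have a DLT, and the qualifying results are "0 of 1 (dose level 1-3) or 0 of 3 (dose level 4-10), 1 of 6 patients (all dose levels requiring additional enrollment"). On such a result, "then enrollment of the next cohort may commence with approval from the Medical Monitor". Escalation stops when at least 33% have a DLT, and the bracket that explains this reads two or more "of up to 6 patients) within a cohort experience a DLT in the DLT window, then the MTD will have been exceeded". The consequence is "then the MTD will have been exceeded and the previous dose level will be considered the MTD". Levels 1-3 enrol one patient each, and levels 4-10 are labelled 3+3. At levels 1-3 a separate clause applies: if a Grade 2 or higher "treatment-related AE is experienced during the DLT window of 6 weeks, then dose escalation schema will convert to a 3+3 design".

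Definition of Dose-Limiting Toxicity covers "any of the following AEs occurring during Cycle 1 (6-week length"), whatever the Investigator's attribution, unless the event clearly has an extraneous cause. The last item on its list is "Any other treatment-related toxicity that results in delay of Cycle 2 administration of CTT1403 by" more than 21 days, and/or toxicity judged by the Investigator and the Sponsor's "medical representatives to be dose-limiting". Study Design sets the cycle length at 6 weeks.

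**The concern.** Finding the MTD is a primary objective of this first-in-human study, so the same data should lead every reader to the same decision.

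**(a) Threshold.** The percentage and the count are presented as one rule, but they give different answers at one DLT in three, the result for which a 3+3 design exists. Stopping there is the cautious direction for patients, but it can set the MTD too low. At levels 1-3 the conversion clause needs a treatment-related event, whereas a DLT counts regardless of attribution. A DLT judged unrelated, but not clearly extraneous, therefore falls outside the clause. At level 1 the percentage would also name a previous dose level that does not exist.

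**(b) Timing.** One listed DLT depends on what happens after the window on which the escalation decision is taken. The next, higher dose can be opened while that DLT is pending. No section tells the committee to wait, or says how a DLT confirmed after escalation changes the decision.

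**Working it through.** **Inputs.** The two lists and cohort sizes come from Dose-Escalation Period, the delay criterion from Definition of Dose-Limiting Toxicity, and the 6-week cycle from Study Design. The documents give no DLT rates, so every rate p below is an assumption, shown over a range.

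**Step 1: do the percentage and the count agree?**

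| DLTs / patients | Proportion | At least 33%? | At least 2 DLTs? | In escalate list? |
|---|---|---|---|---|
| 0/1, 0/3 | 0% | no | no | yes |
| 1/6 | 16.7% | no | no | yes |
| 2/6 | 33.3% | yes | yes | no |
| 2/3 | 66.7% | yes | yes | no |
| **1/3** | 33.3% | **yes** | **no** | no |
| **1/1** | 100% | **yes** | **no** | no |

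The equivalence is not reproduced at 1/3 and 1/1. Because 1/3 and 2/6 are the same proportion, no percentage cut-off can expand on one and stop on the other.

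**Step 2: how often does it matter at one three-patient level?**

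- Exactly one DLT in three: 3p(1-p)^2.
- Stop, percentage read literally: 1-(1-p)^3.
- Pass under 3+3: E(p) = (1-p)^3 + 3p(1-p)^5. Stop: 1-E(p).
- The two stopping probabilities differ by 3p(1-p)^5, the chance of one DLT in the first three and none in the next three.

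| p | Exactly 1 of 3 | Stop, percentage | Stop, 3+3 | Difference |
|---|---|---|---|---|
| 5% | 0.135 | 0.143 | 0.027 | 0.116 |
| 10% | 0.243 | 0.271 | 0.094 | 0.177 |
| 20% | 0.384 | 0.488 | 0.291 | 0.197 |
| 30% | 0.441 | 0.657 | 0.506 | 0.151 |

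**Step 3: when is the delay DLT established?** With a 6-week cycle the window is Days 1-42 and Cycle 2 is due on Day 43. A 21-day delay reaches 43 + 21 = Day 64, so a longer one is established once Day 64 has passed without a dose. That is 64 - 42 = 22 days after the window closes.

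**Step 4: effect on opening the next cohort.** Let s be the share of DLTs that are delay-type and not yet counted at review, and q = p(1-s) the DLT rate visible for an unresolved patient. Suppose starts are at least 22 days apart, so that only the last of each three patients is unresolved. With A = (1-p)^2(1-q), the chance of opening the next cohort is A + A[2p(1-p)^2 + q(1-p)^2].

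For example, at p = 0.20 and s = 1/3, q = 0.1333 and A = 0.64 x 0.8667 = 0.5547. The bracket is 0.2560 + 0.0853 = 0.3413, and 0.5547 x 1.3413 = 0.744.

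| p | All DLTs known, E(p) | s = 1/3 | s = 1/6 |
|---|---|---|---|
| 10% | 0.906 | 0.919 | 0.913 |
| 20% | 0.709 | 0.744 | 0.727 |
| 33% | 0.434 | 0.488 | 0.462 |

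The last column also describes a one-third share of which half is waited for or declared early. The one-third share is itself an assumption.

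**Step 5: how often would the fix for (b) cause a wait?** The chance that a three-patient cohort has at least one delay-type DLT, at a one-third share, is 1-(1-p/3)^3 = 0.097, 0.187 and 0.295 at p = 10%, 20% and 33%.

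**The case against.** On (a), the reply is that nobody would apply the percentage literally. The 3+3 label appears in the dose table and the text, the bracket says two or more, and 1 of 6 is listed as a pass. If 1 of 3 stopped escalation, 1 of 6 could hardly arise at levels 4-10. That stands: expansion is the clear intent. A reader might infer from the percentage that the trial is designed to stop at one DLT in three, and compound that over levels 4-10 into a very high chance of early stopping. The documents do not support this, so the percentage column in Step 2 shows the cost of a misreading and does not forecast the trial. For 1 of 1, a treatment-related DLT will in practice be at least Grade 2 and trigger conversion. That also stands, leaving only the DLT judged unrelated but not clearly extraneous.

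On (b), the discretionary half of the same item lets the toxicity be declared dose-limiting inside the window. The committee sees all safety data, the toxicity itself is visible with only its duration pending, and opening the next cohort is permitted, not required. All of this is correct, and it limits the effect; but neither waiting nor an early declaration is required. A reader might infer a much larger effect by treating every patient as unresolved at every review. That needs near-simultaneous starts, whereas the second three patients enrol only after a DLT in the first three and the protocol lists a single study center. A reader might also infer a wrong final MTD. The calculation concerns only the opening of the next cohort; nothing bars counting the DLT once it is confirmed.

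**Conclusion.** Both parts hold and should be fixed.

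(a) is a wording error in a threshold that serves a primary objective. The rule as written gives conflicting answers at 1/3 and 1/1. The intended answer at 1/3 is clear, but the sentence does not state it, and that result would arise in 14% to 44% of three-patient cohorts at true DLT rates of 5% to 30%. The gap at levels 1-3 is narrow.

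(b) is a real timing gap of modest size. With staggered starts and a one-third share, the chance of opening the next cohort rises by 1.3, 3.5 and 5.4 percentage points at DLT rates of 10%, 20% and 33%. The effect is small at low rates and larger at the highest rate examined. It would be smaller if the share is lower or the committee uses its discretion. The text and day counts behind both parts are certain; the probabilities rest on assumed DLT rates and, for (b), on the assumed share and spacing of starts.

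**What to change.** **(a)** Delete the percentages and state counts: 0/3, escalate; 1/3, enrol three more at the same level; at most 1/6, escalate; two or more, MTD exceeded. Add that any DLT at levels 1-3, whatever its attribution, expands that level under the same counts. The cost is wording and a check against the limit of 33 escalation patients in Number of Patients (planned). Without any expansion the plan uses 3 + 7 x 3 = 24, leaving 9, or three expansions of three; a single-patient level taken to six uses five of those.

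**(b)** Treat the delay criterion as in-window. When Cycle 2 is held for toxicity, do not open the next cohort until that patient has been dosed, has stopped for a non-toxicity reason (progression, withdrawal or the 23 Gy kidney limit), or has passed Day 64. The cost is up to about three weeks, and only in those cases. Holds that become delay-type DLTs would affect about 10%, 19% and 30% of three-patient cohorts at the rates in Step 5. Shorter holds would add to the number of waits, but each would be briefer.
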